9.5.2. Demographic and Baseline Characteristics

Patient demographic and baseline characteristics will be examined to assess the comparability of the treatment groups and will be summarized using descriptive statistics. For continuous variables, descriptive statistics (number, mean, SD, standard error, median, minimum, and maximum) will be provided. For categorical variables, patient counts and percentages will be provided. Categories for missing data will be presented if necessary.

9.6. Efficacy Analyses

9.6.1. Efficacy Variables

9.6.1.1. Primary Efficacy Variable and Endpoint

The primary efficacy variable and endpoint for this study is the change from baseline in the UHDRS-TMS (defined as the sum of the scores of all UHDRS-TMS subitems) at Month 12/ ET (evaluated at baseline and Months 1, 3, 6 and 12)

9.6.1.2. Secondary Efficacy Variables and Endpoints

The secondary efficacy variables and endpoints for this study are:

- Percent change from baseline in caudate volume at Month 12/ET (evaluated at baseline and Month 12)
- Change from baseline in HD-CAB total score (sum of the standardized sub-components) at Month 12/ET (evaluated at baseline and Months 6 and 12)
- CIBIC-Plus global score at Month 12/ET (evaluated at Months 6 and 12) as compared to baseline (rated by an independent investigator)
- Change from baseline in UHDRS- TFC at Month 12/ET (evaluated at baseline, Months 6 and 12)

9.6.1.3. Exploratory Efficacy Variables and Endpoints

- Change from baseline in brain atrophy as defined by the percentage change in volume in: whole brain volume and white-matter volume at Month 12/ET and absolute change in ventricular volume at Month 12/ET (evaluated at baseline and Month 12)
- Change from baseline in UHDRS- FA at Month 12/ET (evaluated at baseline and Months 6 and 12)
- Change from baseline in Q-Motor assessments at Month 12/ET (evaluated at baseline and Months 1, 3, 6 and 12)
- Change from baseline in mPPT at Month 12/ET (evaluated at baseline and Months 6 and 12)
- Change from baseline in HD QoL and EQ-5D-5L at Month 12/ET (evaluated at baseline and Month 12)
- Change from baseline in WLQ at Month 12/ET (evaluated at baseline and Month 12)
- Change from baseline in HD-CAB sub-components at Month 12/ET (evaluated at baseline and Months 6 and 12):
Symbol Digit Modalities Test (SDMT), Emotion Recognition, Trail Making Test, Hopkins Verbal Learning Test, revised (HVLTR), Paced Tapping at 3 Hz, One Touch Stockings of Cambridge (OTS, abbreviated 10 trial version)
- Change from baseline in CDR-SB at Month 12/ET (evaluated at baseline and Month 12)
- Change from baseline in HADS at Month 12/ET (evaluated at baseline and Month 12)
- Change from baseline in PBA-s at Month 12/ET (evaluated at baseline and Month 12)

9.6.1.4. Pharmacodynamic Analyses

- Change from baseline in microglial activation marker TSPO at Month 12/ET
- Change from baseline in brain MRS metabolite markers of neuronal integrity (NAA) and striatal astrocytosis (myo-inositol) at Month 12 in putamen and frontal white matter
- Change from baseline in soluble biomarkers at Months 6 and 12
- Change from baseline in monocyte gene expression and/or proteomic profile at Month 12.

9.6.2. Planned Method of Analysis

The full analysis set (see Section 9.3) will be used for all efficacy analyses. Summaries will be presented by treatment group.

9.6.2.1. Primary Efficacy Endpoint Analysis

The change from baseline in UHDRS-TMS, will be analyzed using a Repeated Measures model (SAS® MIXED procedure with REPEATED sub-command). The model will include the following fixed effects: categorical week in trial by treatment interaction, center, and UHDRS-TMS at baseline. The unstructured covariance matrix for repeated observations within patients will be used. In case that the model will not converge, the Maximum-Likelihood (ML) estimation method will be used instead of the default Restricted ML (REML). If the model still does not converge then a simpler covariance structures with less parameters will be used, according to the following order: Heterogeneous Autoregressive(1) [ARH(1)], Heterogeneous Compound Symmetry (CSH), Autoregressive(1) [AR(1)], and Compound Symmetry (CS). The estimated mean changes from baseline at the Month 12//Early Termination visit will be compared between the active treatment arms and the placebo arm.

The Hochberg's Step-Up method for multiple comparisons between treatment arms will be used to control inflation in type I error rate.

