1.7. Population To Be Studied

Based on the anticipated mode of action (MoA) of laquinimod in HD, an intervention to reduce CNS inflammation as early as possible would be desirable to prevent further neuronal dysfunction and death. However, the rate of progression in signs and symptoms makes it difficult to detect slowing of disease in a feasible way in terms of treatment length in patients without signs of disease. Therefore, patients with clinical symptoms that are measurable, but with a retained functional capacity will be selected. Further, concomitant medications with antipsychotic drugs may confound the data due to side effects in the motor and cognitive domain, and thus these drugs will be disallowed in the study. It is also known that cytosine-adenosine-guanine (CAG) repeat length in the mutant huntingtin gene influence disease progression and course. To reduce variability in the study, patients will be selected from a pre-defined range of CAG repeat lengths frequently observed in the clinic.

Thus, the target patient population will be adult patients, with a CAG repeat length between 36 and 49, and the basic eligibility criteria will select a patient population with symptoms of HD, as assessed by a Unified Huntington's Disease Rating Scale Total Motor Score (UHDRS-TMS) >5 , but with a largely retained functional capacity, as assessed with a HDRS-Total Functional Capacity (UHDRS-TFC) score ≥ 8 . This will recruit a symptomatic early HD patient population.

The criteria for study eligibility are described in Section 4.1 and Section 4.2, respectively.

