3.2.8. Pharmacogenomic Measures and Endpoints

Pharmacogenomic (PGx) assessment will include CAG repeats analysis in the huntingtin gene and might include other DNA variations and RNA expression patterns potentially associated with clinical treatment responses to laquinimod (e.g. clinical effect, pharmacokinetics, tolerability, and safety features or disease susceptibility and severity features). The final list of genes that might be investigated will be selected in a later stage before the analysis so as to allow updating with new scientific information. Genomic analysis could also include a sequencing of the whole genome if required.

The CAG repeat length in the huntingtin gene will be established by a central laboratory for all patients, as part of the screening process to determine eligibility for the study. This will be done also for patients where a historical CAG repeat length result is available. If during this screening process a CAG repeat length result that differs from the patient's historical result is obtained, the central laboratory results should be used for determining eligibility. The exact CAG repeat length will not be available to the sites, only to the Sponsor. The central laboratory report will only note if the patient is within the eligibility criteria range (36-49 inclusive) or not. This will be explicitly explained and noted in the ICF of the patient. In either case, the investigator should review the CAG repeat results with the patient at the baseline visit, or at an unscheduled visit if a baseline visit will not take place.

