4. SELECTION AND WITHDRAWAL OF PATIENTS

4.1. Patient Inclusion Criteria

Patients may be included in the study only if they meet all of the following criteria:

- a. **[New criterion]** Documentation of prior positive genetic testing for HD, or a clinical diagnosis of symptomatic HD (Diagnostic Confidence Level 4).
- b. **[Revision 1]** Presence of 36-49 CAG repeats, inclusive, in the huntingtin gene based on centralized CAG testing during screening.
- c. Male or female between 21-55 years of age, inclusive, with an onset of HD at or after 18 years of age.
- d. **[Revision 1]** Women of child-bearing potential (women who are not post menopausal or who have not undergone surgical sterilization) must practice an acceptable method of birth control for 30 days before taking the study treatment, and 2 acceptable methods of birth control during all study duration and until 30 days after the last dose of treatment was administered. Acceptable methods of birth control in this study include: Intrauterine device, barrier method (condom or diaphragm with spermicide) and hormonal methods of birth control (e.g., oral contraceptive, contraceptive patch, long-acting injectable contraceptive).
- e. A sum of >5 points on the UHDRS-TMS at the screening visit
- f. UHDRS-TFC \geq 8 at the screening visit.
- g. Able and willing to provide written informed consent prior to any study related procedure being performed at the screening visit. Patients with a legal guardian should be consented according to local requirements.
- h. Willing to provide a blood sample for genomic CAG analysis at the screening visit.
- i. Willing and able to take oral medication and able to comply with the study specific procedures.
- j. Ambulatory, being able to travel to the study centre, and judged by the investigator as likely to be able to continue to travel for the duration of the study
- k. Availability and willingness of a caregiver, informant, or family member to provide input at study visits assessing CIBIC-Plus, CDR-SB, PBA-s and HD-QoL. A caregiver is recommended to be someone who attends to the patient at least 2 to 3 times per week for at least 3 hours per occasion, and the suitability of the caregiver should be judged by the investigator.
- l. For patients taking allowed antidepressant medication, the dosing of medication must have been kept constant for at least 30 days before baseline and must be kept constant during the study.

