9.6.2.2. Secondary Efficacy Endpoints Analyses

According to the hierarchical method to control inflation in type I error rate for multiple endpoints, any statistically significant dose that will be observed in the primary analysis will continue to be tested for the secondary endpoints at an alpha level of 5%, according to the secondary endpoints order.

The secondary efficacy endpoints: change from baseline in HD-CAB total score and change from baseline in UHDRS- TFC, will be analyzed in the same way as the primary efficacy endpoint except that the efficacy endpoint evaluation at baseline will be included in the model instead of baseline UHDRS-TMS.

The CIBIC-Plus will be analyzed in the same way as the primary efficacy endpoint except that the baseline CIBIS (Clinician's Interview-Based Impression of Severity) will be included in the model as the efficacy measure at baseline.

The percent change from baseline to Month 12/Early Termination in caudate volume will be analyzed using an Analysis Of Covariance (ANCOVA) model (SAS® MIXED procedure). The model will include the following fixed effects: treatment, center, and caudate volume at baseline.

The estimated means at the Month 12 visit will be compared between the active treatment arms and the placebo arm. Early terminated patient observation will have their Last Observation Carried Forward (LOCF).

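### An efficiency improvement: CAG repeat length, which the protocol calls prognostic and the sponsor holds for every patient, is left out of the primary UHDRS-TMS model and the caudate ANCOVA

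*Protocol*

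**What the plan says.** Section 9.6.2.1 fixes the terms of the primary model: "The model will include the following fixed effects: categorical week in trial by treatment interaction, center, and UHDRS-TMS at baseline". The outcome is change from baseline in UHDRS-TMS, "evaluated at baseline and Months 1, 3, 6 and 12", and the arms are compared at Month 12. For percent change in caudate volume, the first-listed secondary endpoint, Section 9.6.2.2 says: "The model will include the following fixed effects: treatment, center, and caudate volume at baseline". The synopsis gives the same two lists.

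Section 1.7 describes CAG "repeat length in the mutant huntingtin gene influence disease progression and course" and names the means of control: "To reduce variability in the study, patients will be selected from a pre-defined range of CAG repeat lengths frequently observed in the clinic". Section 4.1 sets the range at 36 to 49 repeats, "in the huntingtin gene based on centralized CAG testing during screening".

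Section 3.2.8 adds: "The CAG repeat length in the huntingtin gene will be established by a central laboratory for all patients", and "The exact CAG repeat length will not be available to the sites, only to the Sponsor".

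Section 9.6.2.4 plans no sensitivity analysis, so the protocol plans no CAG-adjusted efficacy comparison elsewhere. Sections 9.6.2.2 and 9.6.2.3 define the models for HD-CAB total score, UHDRS-TFC, CIBIC-Plus and the repeatedly measured exploratory endpoints by reference to the primary model, changing only the baseline term.

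**The concern.** Both endpoints measure 12-month change, which is the progression that Section 1.7 says CAG repeat length affects. The value is known before randomization, comes from one central laboratory, is an entry requirement and so should be complete, and is in the sponsor's hands. Restricting entry to 36 to 49 repeats narrows the variation but leaves whatever lies within that range. If CAG explains variance in 12-month change beyond center and the baseline value, that variance stays in the error term, and the confidence intervals are wider than the collected data allow.

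The model terms are not a detail left to the statistical analysis plan. The protocol lists them itself, while it explicitly defers imputation rules (Section 9.4) and center pooling (Section 9.6.2.5).

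**Working it through.** **Inputs (Section 9.2).** 100 patients per arm; UHDRS-TMS difference 2.5 points, SD 6.2; caudate difference 0.95 percentage points, SD 2.36; type I error 5%. Sidedness is not stated. Two-sided is used here because one-sided does not reproduce the plan: it gives 77 per arm.

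**The plan's own figure.** With n = 2(1.960 + 0.842)²(SD/difference)²:
- UHDRS-TMS: 2 × 7.849 × (6.2/2.5)² = 96.5, so 97 per arm.
- Caudate: 2 × 7.849 × (2.36/0.95)² = 96.9, so 97 per arm.

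At 100 per arm, the noncentral t with 198 degrees of freedom gives 81.0% for UHDRS-TMS (standardized difference 2.5/6.2 = 0.403) and 80.9% for caudate (0.95/2.36 = 0.403). The stated 80% with about 100 per arm reproduces without CAG.

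**Adding CAG.** Let R² be the share of Month 12 residual variance that CAG explains after center and the baseline value. The documents give no R², so a range is assumed. The adjusted variance is SD² × (1 − R²) × (1 + 1/196), where the last factor is the price of estimating one slope, and the test has 197 degrees of freedom. With complete data, a CAG-by-visit term costs the Month 12 contrast only its own Month 12 slope, so the same formula serves both endpoints.

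| Assumed R² | UHDRS-TMS power | Caudate power |
|---|---|---|
| no CAG term | 81.0% | 80.9% |
| 0% | 80.8% | 80.7% |
| 1% | 81.2% | 81.0% |
| 2% | 81.6% | 81.4% |
| 5% | 82.7% | 82.6% |
| 10% | 84.7% | 84.6% |

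Power is per comparison with placebo at 5%, as in the plan's own calculation. Break-even is at R² of about 0.5%, where (1 − R²)(1 + 1/196) = 1.

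**Confidence-interval half-width**, 1.96 × SD × √((1 − R²) × 1.0051 × 2/100):
- UHDRS-TMS: 1.72 points without CAG; 1.71, 1.68 and 1.63 at R² of 1, 5 and 10%.
- Caudate: 0.654 without CAG; 0.653, 0.639 and 0.622 at the same values.

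**The case against.** The strongest reply is that nothing here is wrong. A model with center and the baseline value is valid, and the stated power reproduces without CAG. Section 1.7 raises CAG to justify limiting its range, and the protocol then does so; it never promises covariate adjustment. All of this stands, so the point is an improvement and not a contradiction. What it does not answer is the variation left inside 36 to 49 repeats, which an available baseline value could help to explain.

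A second reply is that the benefit is unknown. This also stands. At R² of 1% the gain is about 0.2 power points, no larger than the worst-case loss. Sections 3.2.6.2 and 9.9.2 list CAG as a possible covariate for pharmacokinetics, but that says nothing about residual variance in UHDRS-TMS or caudate change.

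A third is that CAG would get a slope for each visit while baseline UHDRS-TMS enters as a main effect only. The documents do not show that the CAG effect differs by visit. The by-visit form is proposed because the comparison is made at Month 12, and it lets that visit have its own slope at little cost.

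A reader might go further and infer that omitting a prognostic variable biases the treatment effect. It does not: CAG is fixed before randomization, so chance imbalance is already covered by the standard error. Dropout related to CAG beyond the modelled terms could bear on the missing-data assumption, but the documents give no sign of it.

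**Conclusion.** The point holds as an optional efficiency improvement. There is no bias in the randomized comparison, no inflation of type I error and no sample-size error. On the assumed range of 0 to 10%, the effect on power runs from a loss of about 0.2 points to a gain of about 3.7 points for each endpoint.

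This rests on complete data, 100 per arm, two-sided 5%, a linear CAG effect, and planning SDs that do not already reflect adjustment for CAG; the protocol does not say whether 6.2 and 2.36 are adjusted. The gain may be negligible if entry restriction, center and the baseline value already absorb the CAG effect. It would be larger than shown if R² exceeded 10%. The documents settle neither, so they do not support a claim that the trial forgoes a material amount of power.

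**What to change.** Before the three continuing arms are unblinded, pre-specify continuous central-laboratory CAG repeat length as a covariate:
- in Section 9.6.2.1, as CAG-by-visit in the UHDRS-TMS model, with one slope each for Months 1, 3, 6 and 12;
- in Section 9.6.2.2, as a single term in the caudate ANCOVA.

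Because Sections 9.6.2.2 and 9.6.2.3 borrow the primary model, a change there would pass by default to HD-CAB total score, UHDRS-TFC, CIBIC-Plus and the exploratory repeated-measures endpoints. State explicitly whether the CAG term carries over. Carrying it over fits the progression rationale; otherwise name its omission as an exception alongside the baseline term. Bring the synopsis into line. If the sponsor prefers not to adjust, a sentence giving the reason is enough.

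The cost is about 4 degrees of freedom in the UHDRS-TMS model and 1 in the caudate ANCOVA, at worst about 0.2 power points per Month 12 comparison. No covariance parameters are added, so the convergence fallback order stays as written. No new data are needed, and sites still need not see the exact value.

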- Starting after visit Month 3 a urine β -hCG test will be performed at home in women of child-bearing potential every 28 (\pm 2) days. The patient will be contacted by telephone within 72 hours after the scheduled test is to be performed and asked specific questions regarding the test. In case of suspected pregnancy (positive urine β -hCG test result), the caller will make sure that the study drug has been discontinued and the subject will be instructed to arrive to the site as soon as possible (within 10 days) with all remaining study drugs capsules.
- When applicable, patients will be screened for drug substances in urine and/or CDT level in blood at screening to confirm abstinence in former (more than 12 months from screening) alcohol and/or drug abusers.
- Blood for analysis of cytokines and other soluble proteins will be collected at baseline, and at Months 6 and 12, concomitant with other blood draw procedures.
- ECG will be performed at screening, baseline, and at Months 1, 3, 6, and 12, and will be centrally evaluated.
- Blood sample for genomic analysis and CAG repeat length determination will be drawn at screening.
- Adverse Events (AEs) will be monitored throughout the study.
- Suicidality will be monitored throughout the study through administration of the C-SSRS
- Concomitant medications will be monitored throughout the study.
- All subjects will undergo MRI scans at baseline and Month 12.
- Motor function evaluations (UHDRS-TMS and Q-Motor) will be performed at screening, baseline and at Months 1, 3, 6 and 12.
- Functional capacity evaluations (UHDRS-TFC and mPPT) will be performed at baseline and at Months 6 and 12. The UHDRS-TFC is also performed at screening.
- Clinical global impression will be evaluated by an independent rater using the Clinician's Interview-Based Impression of Severity (CIBIS) process at baseline and CIBIC-Plus at Months 6 and 12
- Psychiatric and behavioral evaluations (PBA-s and HADS) will be done at baseline and at Month 12.
- Cognitive capacity will be evaluated at screening, baseline and at Months 6 and 12, by administration of the HD-CAB (SDMT, Emotion Recognition, Trail Making Test, HVLT-R, Paced Tapping at 3 Hz, OTS).
- A reduced battery comprised of the SDMT and Trail Making Test will be performed at Months 1 and 3.

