3.5. Duration of Patient Participation

Subjects are expected to participate in this study for approximately 14 months, consisting of a screening period of 2 weeks up to 5 weeks, a double-blind treatment period of 12 months and a 1 month follow-up period.

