3.11.2. Procedures Before Study Drug Treatment and Randomization (Baseline [Visit 2])

Patients who meet the inclusion/exclusion criteria at Visit 1 will continue to Visit 2, when baseline evaluations will be conducted.

The following procedures will be performed at Visit 2 in patients who continue to meet the inclusion/exclusion criteria:

- review inclusion/exclusion criteria
- perform clinical laboratory tests
- estimated creatinine clearance calculation
- clinical hematology

- anemia panel (blood smear, serum iron, ferritin, total iron binding capacity, folic acid, haptoglobin, interleukin [IL]-1, IL-6, interferon [IFN]- γ , tumor necrosis factor [TNF]- α , and hepcidin) and B12
- lipid profile
- thyroid function (T3, T4, TSH)
- blood sample for soluble biomarkers (cytokines)
- blood sample for gene expression analysis
- blood sample for monocyte analysis (**Only at selected sites in a subgroup of patients**)
 - Blood sample for monocyte collection and analysis has to be done in accordance with the laboratory manual;
 - For UK patients, the sample can be drawn prior to the baseline visit, as it coincides with the PET scan visits
- perform full physical examination (including weight)
- perform vital signs measurements
- ECG – in triplicate (approximately 10 \pm 5 minutes apart)
- urine β -HCG in women of child-bearing potential
 - The urine test should be conducted at the site to allow randomization. A serum β -HCG test should also be used to confirm the urine test; however, the randomization should be performed based on the results of the urine pregnancy test.
- serum β -HCG in women of child-bearing potential
- additional urine β -HCG in women of child-bearing potential at PET facilities (**Only in a subgroup of patients**)
- Ascertaining use of acceptable contraception
- C-SSRS (since last visit version)
- MRI scan
 - The baseline MRI can be performed at the screening visit, but no later than 7 days prior to baseline.
 - If anxiolysis is required in order to perform the MRI scan, the scan should be performed at the end of the study visit day.
- MRS scan (**Only at selected sites in a subgroup of patients**)
- PET scan (**Only in a subgroup of patients**)
 - The PET scan can be done at any time prior to the date of the baseline visit, after eligibility of the patient has been confirmed.
 - Patients taking benzodiazepines should be instructed to stop taking them for 3 days prior to having the PET scan.
- UHDRS-TMS
- UHDRS-TFC
- UHDRS-FA
- mPPT

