9.2. Sample Size and Power Considerations

The study aims to detect potential beneficial effects in deteriorating clinical signs and symptoms. Based on previous studies in patients with HD, the UHDRS-TMS has been shown to be one of the more sensitive clinical measures to detect decline in symptoms of HD. It is estimated that approximately 100 patients per arm will enable a power of 80% to detect a beneficial effect compared to placebo, of 2.5 points or more in the change from baseline in UHDRS-TMS of an active laquinimod arm, assuming SD of 6.2 and type I error of 5%.

As the intention is to investigate laquinimod as a treatment with the potential to slow disease progression and prohibit neuronal death in the CNS, the study should also be sized to be able to detect changes in brain atrophy rate after treatment with laquinimod. One of the most sensitive measures to detect brain atrophy over time in patients with HD is change in the caudate volume.

It is estimated that approximately 100 patients per arm will enable a power of 80% to detect a beneficial effect of 0.95 (30% of the estimated decline in placebo) or more in the percent change from baseline in caudate brain atrophy of an active laquinimod arm compared to placebo, assuming SD of 2.36 and type I error of 5%.

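### The primary UHDRS-TMS model adjusts for the Visit 2 score only; a screening score already collected before randomization could be added as a second covariate, for a precision gain at almost no cost

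*Protocol*

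**What the plan says.** The synopsis schedules the motor scale twice before the first dose: "Motor function evaluations (UHDRS-TMS and Q-Motor) will be performed at screening, baseline and at Months 1, 3, 6 and 12". Section 4.1 makes the first of these scores an entry requirement: "A sum of >5 points on the UHDRS-TMS at the screening visit". Section 3.5 describes participation as "consisting of a screening period of 2 weeks up to 5 weeks" followed by treatment, so the two scores are nominally 2 to 5 weeks apart. Sections 3.11.1 and 3.11.2 list UHDRS-TMS at Visit 1 and again at Visit 2.

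Section 9.6.1.1 defines the primary endpoint as the change from baseline in UHDRS-TMS "at Month 12/ ET (evaluated at baseline and Months 1, 3, 6 and 12", without mention of screening. Section 9.6.2.1 gives the fixed effects of the repeated measures model as "categorical week in trial by treatment interaction, center, and UHDRS-TMS at baseline", and the synopsis repeats them. Section 9.6.2.2 carries the model over to the secondary endpoints "except that the efficacy endpoint evaluation at baseline will be included in the model instead of baseline UHDRS-TMS". Section 9.6.2.4 plans no sensitivity analyses. No section gives the screening TMS a role in an analysis or defines baseline as a mean of the two scores.

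The protocol defers other items to the statistical analysis plan, such as imputation rules (9.4) and center pooling (9.6.2.5). It fixes the covariates itself.

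**The concern.** Section 6.3.3 acknowledges intra- and inter-rater variability in scales such as UHDRS-TMS. If one score carries visit-level error, two pre-dose scores predict the Month 12 score better than one. The second score would then lower the residual variance of the Month 12 contrast. It cannot bias the treatment comparison, because both scores precede randomization.

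At stake is the precision of the contrast that gates everything else. Under 9.7, a dose proceeds to the secondary endpoints only if it is significant on the primary endpoint. The score that could sharpen this comparison is already collected.

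**Working it through.** **Inputs from the protocol (9.2):** difference 2.5 points, SD of change 6.2, about 100 per arm, type I error 5% (two-sided assumed, since sidedness is not stated). The stated result is "approximately 100 patients per arm will enable a power of 80% to detect a beneficial effect".

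**Step 1. The plan's own figure.** Standard error = 6.2 × √(2/100) = 0.877. Then 2.5/0.877 = 2.851, and 2.851 − 1.960 = 0.891, which gives power 81.4% (81.0% by noncentral t). Required n = 2 × 6.2² × (1.960 + 0.842)² / 2.5² = 96.5, so 97 per arm. The stated 80% with about 100 per arm is reproduced.

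**Step 2. Assumptions needed.** Let σ be the cross-sectional SD of TMS, equal at baseline and Month 12, and r the screening-to-Visit 2 correlation. The protocol gives neither. I take σ = 10 to 14 and r = 0.90 to 0.98. An SD of change of 6.2 implies a baseline-to-Month 12 correlation ρ = 1 − 6.2²/(2σ²): 0.808, 0.867 and 0.902 for σ = 10, 12 and 14.

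**Step 3. Residual variance if screening predicts Month 12 as well as Visit 2 does.**
- One score: σ²(1 − ρ²).
- Two scores: σ²(1 − 2ρ²/(1 + r)).

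Example, σ = 12 and r = 0.95: 1 − 0.7509 = 0.2491 against 1 − 2 × 0.7509/1.95 = 0.2299. The ratio is 0.923, a reduction of 7.7%.

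| σ | r | Variance reduction | Power, one score | Power, two scores |
|---|---|---|---|---|
| 10 | 0.90 | 9.9% | 85.1% | 88.5% |
| 10 | 0.95 | 4.8% | 85.1% | 86.7% |
| 10 | 0.98 | 1.9% | 85.1% | 85.7% |
| 12 | 0.90 | 15.9% | 83.9% | 89.6% |
| 12 | 0.95 | 7.7% | 83.9% | 86.7% |
| 12 | 0.97 | 4.6% | 83.9% | 85.6% |
| 14 | 0.92 | 18.2% | 83.2% | 89.8% |
| 14 | 0.95 | 11.2% | 83.2% | 87.3% |

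The row σ = 14, r = 0.90 is left out: r would fall below ρ = 0.902, which this model does not allow.

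**Step 4. Screening a weaker predictor than Visit 2.** With a and b the correlations of Visit 2 and screening with Month 12, the explained share is (a² + b² − 2abr)/(1 − r²). For σ = 12, r = 0.95 and a = 0.867, the 7.7% reduction becomes 2.2% if b is 0.02 lower than a, and 0.7% if b is 0.03 lower. Power then goes from 83.9% to 84.7% and 84.2%.

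**Step 5. A second parameterization.** Split 6.2² into twice the visit-error variance plus the variance of true change, with a between-patient SD of 8 to 16. Treat 6.2 as the residual SD given one baseline score, so that power starts at 81%.

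| Visit error as share of change variance | Variance reduction | Power with two scores |
|---|---|---|
| 10% | about 2% | 82% |
| 25% | about 6% | 84% |
| 50% | 10–12% | 85–86% |
| 75% | 15–18% | 87–88% |

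The limiting case, where all of the change variance is visit error, gives 19–23%.

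**Step 6. Effect of selecting on the screening score.** A simulated analysis of covariance, 100 per arm with entry restricted to screening TMS above 5, gave variance reductions of 6%, 10–11% and 16% at error shares of 25%, 50% and 75%. The mean treatment estimate was within about 0.02 points of the truth with either model.

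**The case against.** **No error is shown.** Adjusting for the endpoint's own baseline is conventional and valid, and the stated power is met. This stands. A reader might infer that the planned analysis is biased, or that the trial misses its power target without the change. The documents support neither reading.

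**The size cannot be taken from the documents.** This also stands. Of the quantities that drive the gain, only the SD of 6.2 is given. Section 6.3.3 mentions rater variability without a figure, section 6.1 requires certified raters, and the center term may absorb some rater differences. A reader might take 5% to 18% as an established gain. It is not: the 18% row in Step 3 requires (1 − 0.92)/(1 − 0.902), about 82%, of the 12-month change variance to be visit error, a strong assumption in a progressive disease.

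**The two scores may not be equivalent replicates.** Section 3.11.1 allows routine-care evaluations during screening to replace protocol-specific ones and foresees an extended screening period. Step 4 shows how quickly the gain shrinks when screening is the weaker predictor. The covariate remains unbiased, but the benefit may be slight.

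**The idea does not extend to every endpoint scored at screening.** Table 3 says that the screening HD-CAB is there to reduce practice effects, so it is a practice run and not a replicate. HD-CAB (6.2.2) and Q-Motor (6.3.3) are done only at equipped sites and in patients able to perform them, and neither is an eligibility score. Screening values may be missing, and a patient without a covariate value drops out of the model. UHDRS-TFC is different, being an eligibility score like TMS, though no gain has been calculated for it.

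**Conclusion.** The point holds as a recommendation to improve efficiency. A screening UHDRS-TMS exists for every properly enrolled patient, the fixed covariate list omits it, and the protocol gives it no use beyond eligibility. Adding it leaves validity untouched.

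The gain lies between about zero and 18% of the residual variance. It is about 5% to 18% when visit-to-visit error is substantial, and about 0% to 5% when TMS is very reliable (r of 0.97 to 0.98 with σ of 10 to 12) or when screening predicts Month 12 slightly less well than Visit 2. At 100 per arm that is roughly 0 to 6 points of power, 6.6 in the most favorable row of Step 3. These figures assume a two-sided 5% test of one dose against placebo and no dropout. The case for acting is the negligible cost, not a demonstrated large benefit.

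**What to change.** Before unblinding, add screening UHDRS-TMS to 9.6.2.1 and the synopsis as a second continuous covariate beside Visit 2 UHDRS-TMS. Keep change from Visit 2 as the endpoint. State a rule for any patient without a screening score, so that nobody is lost from the model.

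Because 9.6.2.2 and 9.6.2.3 define their models by reference to the primary one, say there explicitly that screening TMS is not carried over. For UHDRS-TFC, the screening TFC score may be added in the same way. Leave the HD-CAB and Q-Motor models as they are.

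The cost is a few lines of text and one degree of freedom, with no new data, visits or patient burden. It needs to be prespecified, since a covariate added after unblinding would look data-driven.
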